9.2. Sample Size Determination

Time to clinical improvement

A randomized, double-blind, placebo-control study evaluating remdesivir in 1063 hospitalized patients with COVID-19 reported 606 recoveries, with a median time to recovery of 11 days and 15 days in the remdesivir and placebo groups, respectively (remdesivir package insert). Recovery was defined as the first day on which the subject satisfies one of the following 3 categories from the ordinal scale: 1) Hospitalized, not requiring supplemental oxygen - no longer requires ongoing medical care; 2) Not hospitalized, limitation on activities and/or requiring home oxygen; 3) Not hospitalized, no limitations on activities (<https://clinicaltrials.gov/ct2/show/NCT04280705>).

Assuming the median time to clinical improvement, defined as no longer requiring oxygen support or hospital discharge whichever occurs first, will be 12-15 days in the placebo group, and that at least 75 of the planned 120 subjects enrolled meet the clinically improved criteria, the study will have at least 80% power to detect a 50% reduction in the time to clinical improvement, (i.e., hazard ratio of 0.5).

Change from baseline to Day 10 or hospital discharge if sooner in the ratio of hemoglobin oxygen saturation to inspired oxygen fraction (SpO_2/FiO_2).

A prospective observational cohort study of non-intubated moderate to severe ARDS patients (Ding, 2020) reported the partial pressure of oxygen (PaO_2)/ FiO_2 ratio for 10 patients, which gave a mean and standard deviation of 147 ± 46 mm Hg. Converting to a SpO_2/FiO_2 ratio gives a mean and standard deviation of 192 ± 39 using the equation reported by Rice et al. (2007) (Rice, 2007).

Assuming a standard deviation of 40 in the SpO_2/FiO_2 ratio, a sample size of 120 subjects (80 active, vs 40 control) will provide approximately 90% power to detect a treatment difference in

the SpO₂/FiO₂ ratio of 25 or greater, based on a two-sample t-test with a two-sided 5% significance level

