Assuming the median time to clinical improvement, defined as no longer requiring oxygen support or hospital discharge whichever occurs first, will be 12-15 days in the placebo group, and that at least 75 of the planned 120 participants enrolled meet the clinically improved criteria, the study will have at least 80% power to detect a 50% reduction in the time to clinical improvement, (i.e., hazard ratio[BLD2660/Placebo] of 0.5) with a two-sided 5% significance level.

The total number of events (d) is estimated based on the following formula

$$d = \frac{(z_{\alpha/2} + z_{\beta})^2}{\pi(1 - \pi)\theta^2}$$

where $z_{\alpha/2}$ and z_{β} are the value from a standard normal distribution, π is the proportion of participants randomized to control, $1 - \pi$ is the proportion of participants randomized to active and θ is the inverse of the log hazard ratio, as we are modeling improvement. The total number of participants is then calculated as the number of events divided by the probability of observing the event during the study. For this study $\alpha = 5\%$, $\beta = 20\%$, $\pi = 1/3$ and $\theta = 1/\log(0.5)$ and the probability of observing an event is 0.60.

Change from baseline to Day 10 or hospital discharge if sooner in the ratio of hemoglobin oxygen saturation to inspired oxygen fraction (SpO₂/FiO₂).

A prospective observational cohort study of non-intubated moderate to severe ARDS participants (Ding, 2020) reported the partial pressure of oxygen (PaO₂)/FiO₂ ratio for 10 participants, which gave a mean and standard deviation of 147 ± 46 mm Hg. Converting to a SpO₂/FiO₂ ratio gives a mean and standard deviation of 192 ± 39 using the equation reported by Rice et al. (2007) (Rice, 2007).

Assuming a standard deviation of 40 in the SpO₂/FiO₂ ratio, a sample size of 120 participants (80 active, vs 40 control) will provide approximately 90% power to detect a treatment difference in the SpO₂/FiO₂ ratio of 25 or greater, based on a two-sample t-test with a two-sided 5% significance level.

CONFIDENTIAL

Statistical Analysis Plan [Version 3.0]

The total number of participants (N) is estimated based on the following formula

$$N = \frac{(z_{\alpha/2} + z_{\beta})^2}{\pi(1 - \pi)\theta^2}$$

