where $z_{\alpha/2}$ and z_{β} are the value from a standard normal distribution, π is the proportion of participants randomized to control, $1 - \pi$ is the proportion of participants randomized to active and θ is the standardized effect size we wish to detect. For this study $\alpha = 5\%$, $\beta=10\%$, $\pi=1/3$ and $\theta=0.625$ (i.e., $25/40$).

4. Analysis Sets

For purposes of analysis, the following populations are defined:

Population	Description
Enrolled	All randomized participants
Full Analysis Set (FAS)	All randomized participants who receive at least one dose of study drug. This population will be used for all efficacy analyses
Modified Intent to Treat (MITT)	All randomized participants who receive at least one dose of study drug and one post baseline assessment of the SpO ₂ /FiO ₂ ratio. This population will be used for the primary and secondary endpoints related to improvement in SpO ₂ /FiO ₂ ratio.
Per Protocol Analysis Set (PP)	All randomized participants who receive at least 6 doses of study drug without any major protocol violations that would impact the assessment of the primary efficacy endpoints. This population will be used for efficacy analyses of the primary efficacy endpoints
Safety Analysis Set	All enrolled participants who receive any study drug
PK Analysis Set	All enrolled participants who receive any study drug and have plasma concentration data

5. Statistical Analyses

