The primary efficacy endpoint of change from baseline to Day 10 or hospital discharge if sooner, in the ratio of hemoglobin oxygen saturation to inspired oxygen fraction (SpO₂/FiO₂) will be analyzed using a mixed model for repeated measures (MMRM). The Kenward-Roger method will be used to calculate the denominator degrees of freedom for the test of fixed effects and adjusted standard errors. The model will contain treatment, time and the treatment by time interaction as fixed effects and baseline score, age (years), corticosteroid use (yes vs no) and remdesivir strata as covariates. If age and/or corticosteroid use are not significant at the 5% level, they will be removed from the model. As the follow-up visit schedule for each participant will be variable, the following timepoints will be used; Day 1, Day 2, Day 3, Day 4, Day 5 and Day 10/Discharge. Additional time points (e.g., Days 6-9) may be included if most participants are not discharged prior to Day 10. An unstructured covariance matrix will be assumed to model the within-participant errors. This variance-covariance matrix will be estimated across treatment groups. However, if there is a convergence problem with the unstructured covariance matrix, then alternative covariance structures will be examined (heterogeneous Toeplitz structure, Compound Symmetry) and the one with the best fit as determined by the Akaike information criteria (AIC) (i.e., smallest AIC value) will be used. The least squares means (LS-means) for each treatment, LS-means treatment difference and corresponding confidence interval (CI) for the LS-means difference and p-value for the treatment difference, will be reported at the Day10/Discharge timepoint.

The primary analysis will be conducted using the FAS.

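### Does the 90% power for the SpO2/FiO2 endpoint fail because its SD of 40 comes from levels in 10 ARDS patients?

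*SAP*

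**What the plan says.** SAP section 3 (Sample Size Determination) and Protocol 9.2 size this endpoint in the same way. The starting point is "A prospective observational cohort study of non-intubated moderate to severe ARDS participants", with a PaO2/FiO2 "ratio for 10 participants, which gave a mean and standard deviation of 147 ± 46 mm Hg". A published equation converts this to an SpO2/FiO2 of 192 ± 39. The power sentence then opens "Assuming a standard deviation of 40 in the" ratio and concludes that "a sample size of 120 participants (80 active, vs 40 control) will provide approximately 90% power to detect a treatment difference in the" ratio of at least 25, using a two-sample t-test at two-sided 5%. Protocol 9.2 says the same: "a sample size of 120 subjects (80 active, vs 40 control) will provide approximately 90% power to detect a treatment difference in" the ratio. In the SAP's formula, θ "is the standardized effect size we wish to detect", entered as 25/40 = 0.625.

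The analysis in SAP 5.5.2 is an MMRM of change from baseline with "baseline score, age (years), corticosteroid use (yes vs no) and remdesivir strata as covariates". It reports the LS-means difference at Day 10/Discharge with its confidence interval.

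For the other primary endpoint, the same section assumes that median time to improvement "will be 12-15 days in the placebo group" and sizes for a halving of that time.

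**The concern.** The SD used for sizing is a cross-sectional SD of the ratio in a small ARDS group. The quantity that governs power is the residual SD of the Day 10/Discharge value after adjustment for baseline, in this trial's patients. Eligibility runs from SpO2 of 94% or below on ambient air up to FiO2 just under 0.75 (Protocol 5.1.1 and 5.1.2), which is wider than the source group.

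The figure also has almost no margin, since power drops below 90% once the SD passes 39.5. The recovery assumption in the same section suggests that, by Day 10, some patients will be on room air and others still on oxygen, which could spread the ratio well beyond an SD of 40.

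Either primary endpoint can declare success alone, and this is the only sizing argument for this one. If the SD were much larger, a reader who trusted the 90% figure might take a null result as ruling out a 25-point benefit when it does not.

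**Working it through.** **1. The plan's own figure.** Inputs from SAP section 3: difference 25, SD 40, 80 vs 40, two-sided 5%.

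- SAP formula: N = (1.960 + 1.282)² / [(1/3)(2/3)(0.625²)] = 121.0, against 120 planned.
- Standard error = 40 × √(1/80 + 1/40) = 7.75, and 25/7.75 = 3.23. Power from the noncentral t (118 df) is 89.3%; the normal approximation gives 89.8%.

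The stated figure reproduces.

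**2. Sensitivity to the SD, with the difference held at 25.**

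| Residual SD | Power | 95% CI half-width |
|---|---|---|
| 35 | 96% | 13 |
| 40 | 89% | 15 |
| 50 | 73% | 19 |
| 60 | 57% | 23 |
| 80 | 36% | 31 |

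Power is 90% at SD 39.5, 80% at 45.7 and 50% at 65.3. An SD of 39 from 10 patients has a 95% interval of 39 × √(9/χ²₉) = 26.8 to 71.2 (normality assumed), which corresponds to power from 99.8% down to 44%.

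**3. Levels against change.** Suppose 40 is the SD of levels at both times, with baseline correlation r. The baseline-adjusted SD is 40 × √(1 − r²).

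- r = 0: 40.0, power 89%.
- r = 0.5: 34.6, power 96%.
- r = 0.7: 28.6, power 99%.

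The planned model adjusts for baseline, so using a levels SD gives a floor on power, not a ceiling. An unadjusted change score would be worse for r below 0.5 (SD 56.6 at r = 0), but that is not the planned analysis.

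**4. Is SD 40 too small for this population?** The documents give no direct figure, so this step needs assumptions: exponential recovery, SpO2 of 94% throughout, room-air FiO2 of 0.21, all recovered patients on room air, and the rest spread evenly over 1–3 or 1–6 L/min by nasal cannula (FiO2 from the SAP 5.5.1 table).

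- Placebo recovered by Day 10: 1 − 0.5^(10/15) = 37% to 1 − 0.5^(10/12) = 44%.
- Room air: 94/0.21 = 448. Patients on oxygen: mean 340, SD 40 (1–3 L/min), or mean 288, SD 61 (1–6 L/min). The gaps from room air are 107 and 159 points.
- Placebo Day 10 SD = √[p(1 − p)·gap² + (1 − p)·s²] ≈ 61 or 91 before baseline adjustment. A residual SD of 40 would need r of about 0.75 or 0.90.

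**5. The effect moves with the SD.** In this model the spread comes from the gap between room air and oxygen, and that gap also sets the treatment difference. Doubling the recovery rate, which is how the plan's halved recovery time reads under exponential recovery, gives 60% to 69% of active patients recovered. The difference is then (p₁ − p₀) × gap.

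| Patients still on oxygen | Difference | Power, r = 0.5 | Power, r = 0.7 |
|---|---|---|---|
| 1–3 L/min | 25–26 | 70–76% | 85–90% |
| 1–6 L/min | 37–39 | 70–76% | 85–90% |

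These powers use the normal approximation with each arm's own SD. With 1–6 L/min and r = 0.5, the placebo residual SD is about 79. Holding the difference at 25 gives power of about 37% at that SD, roughly half what the same model gives once its own effect is used.

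**The case for a change.** The strongest case for a change is that the documents nowhere support 40 as the residual SD in this population. The source is tiny and comes from a different group, there is no margin, and the plan's own recovery assumption points to a wider spread. A caveat, a power table by SD and one extra model output would cost little, and the residual SD would be useful because SAP 5.10 says the Phase 2 data feed Phase 3 planning.

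Part of this stands. The SD is an assumption taken from a weak source, no range is shown, and 90% should not be read as robust. In the illustrative model at a correlation of 0.5, power is nearer 70–76%.

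The rest does not carry a change. A careful reader can already see the source, the sample of 10 and a mean of 192, which can only be a level. A power table that fixes the difference at 25 while the SD rises to 80 would mislead, for the reason in step 5. A null result is already protected by the planned interval for the LS-means difference: with an observed difference of 0, the interval excludes 25 only if the residual SD is below about 65, and its width shows this directly. An approximate residual SD can be recovered from that width and the group sizes.

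**Conclusion.** No change to the plan is needed. The stated power is correct for its stated SD (89% at 80 vs 40), and sizing a baseline-adjusted analysis from an SD of levels is not optimistic in itself. The only open question is whether patients in this trial vary more than the source group. The documents cannot answer it: the illustrative Day 10 SDs of about 61 to 91 rest on assumed recovery times, saturations, flow rates and correlations, and under those same assumptions power for the plan's own recovery effect is about 70% to 90%. That does not show an underpowered trial.

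SAP 5.10 records that enrolment had finished, so no sizing decision remains. The 90% figure is best left as the historical design statement. A caveat or an extra output would alter no test, estimate or decision rule, and a null result should be read from the confidence interval already planned in SAP 5.5.2. Analysts can add the residual SD to the study report if it helps Phase 3 planning; nothing in the plan prevents that.

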Hospital discharge readiness assessment		X	X	X	X	X	X		Refer to Section 8.1.5
Clinical status 6-point ordinal scale	X	X	X	X	X	X	X		Refer to Section 8.1.2
State of consciousness	X	X	X	X	X	X	X		Level of consciousness: alert (A), arousable only to voice (V), or pain (P) and unresponsive (U)

Procedure	Screening	Treatment Period			Follow-up			Post-study visit	Notes
		BL	Daily visits [‡]	EOT/ET*			EOS		
Study Day	-3 to -1	1	2-9	10	14	21	28	+60 days from EOS	Baseline (BL); End of Treatment (EOT), Early termination (ET); End of study (EOS) [‡] If a subject is discharged prior to Day 10, they will complete Day 5 and Day 10 visits assessments * This visit will be conducted at hospital discharge, if subject is discharged prior to Day 10
Visit window (days)				±1	±2	±2	±2	±10	
Randomization		X							
Study drug administration		X	X	X					Treatment to be administered during hospitalization only
Study drug accountability			X	X					
AE and SAE review		X	X	X	X	X	X		Adverse event (AEs), Serious AE (SAEs)
Prior and concomitant medication	X	X	X	X	X	X	X		
Survival status					X	X	X	X	

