6. STUDY DRUG

6.1. Study Drugs Administered

For more details on specific indications refer to the BLD-2660 Investigator Brochure (IB).

Table 3: Study Drug Administered

	Active	Control
Drug Name	BLD-2660	Placebo
Type	Drug (small molecule)	Drug
Dose Formulation	Capsules, Hard gelatin size '00'	Capsules, Hard gelatin size '00'
Unit Dose Strength(s)	150 mg	NA
Dosage Level(s)	900 mg BID (6 capsules BID) for a total of 1800 mg per day	NA
Route of Administration	Oral (PO); naso-gastric tube (NGT) may be used in special cases as detailed in Administration instruction below.	
Administration instruction	
Study drug to be taken orally BID:
 
 • Morning dose to be taken at least one hour before food • Evening dose to be taken at least 2 hours after food 
In the case where a subject needs mechanical ventilation, study drug can be administered via an NGT by opening the study drug capsules and suspending the contents in the required amount of water as described in the Pharmacy Manual, then administering through the tube. Lavage with additional 20-30 mL of water to ensure study drug does not stick to the tubing. Do not attempt to administer through a feeding tube.
	
Sourcing	Study drug will be provided to the site centrally by the Sponsor or designated representative.	
Packaging and Labeling	Drug product, both active and placebo, will be supplied in bulk packaging (40 capsules/bottle). Label text will at a minimum include the protocol number, lot number, storage conditions, and Sponsor name and address. Labels comply with regulatory requirements for study drugs.	

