9.3. Population Analysis Set

For purposes of analysis, the following populations are defined:

Population	Description
Full Analysis Set (FAS)	All randomized subjects who receive at least one dose of study drug. This population will be used for all efficacy analyses
Modified Intent to Treat (MITT)	All randomized subjects who receive at least one dose of study drug and one post baseline assessment of the SpO ₂ /FiO ₂ ratio. This population will be used for the primary and secondary endpoints related to improvement in SpO ₂ /FiO ₂ ratio.
Per Protocol Analysis Set	All randomized subjects who receive at least one dose of study drug without any major protocol violations that would impact the assessment of the primary efficacy endpoints. This population will be used for efficacy analyses of the primary efficacy endpoints
Safety Analysis Set	All enrolled subjects who receive any study drug
PK Analysis Set	All enrolled subjects who receive any study drug and have plasma concentration data

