1.2. Study Design

This is a Phase 2 randomized, double-blind, placebo-controlled multicenter study designed to evaluate BLD-2660 as add-on to standard of care (SOC) therapy in hospitalized participants with recently diagnosed COVID-19 compared to SOC treatment.

The study will include a Screening period, a Treatment period, and a Follow-up period.

After signing informed consent form (ICF), potential candidates who are hospitalized for confirmed infection with SARS-CoV-2 will undergo additional screening procedures.

On Day 1, eligible participants will be randomized in 2:1 ratio to one of 2 treatment groups, active or control, as shown in Table 1. Randomization will be stratified by remdesivir at study entry. All participants will receive study drug in combination with SOC over 10 days (through Day 10/end of treatment) or until hospital discharge, if sooner. Participants will be followed for at least 18 days after the last dose of study drug on Days 14, 21 and 28. Participants will be contacted 60 days post-study to collect information on mortality and forced vital capacity (FVC).

CONFIDENTIAL

Statistical Analysis Plan [Version 3.0]

Table 1: Treatment Groups

Treatment Group	Dose Level, Schedule and Route of administration	Number of participants
Active	BLD-2660 900 mg twice per day (BID), oral + SOC	80
Control	Matching placebo, BID, oral + SOC	40

For each participant, the study duration for each study period is expected to last as follows:

Study Period	Duration
Screening period	Up to 3 days
Treatment period	10 days
Treatment Follow-up period	18 days
Post study follow-up period	32 days

Interim analyses are planned when approximately 25%, 50% and 75% of participants have completed the study for the purpose of reviewing safety data and for the purpose of early stopping for efficacy or futility. At the 50% interim analyses, the sample size may be increased.

The final analysis will occur once the last participant enrolled completes the end of study follow-up visit. Data from the post study follow-up visit regarding FVC will be included in the final databased after the final analysis has been completed.

2. Statistical Hypotheses

Two primary statistical hypotheses will be tested. The study will be declared a success if either of the hypotheses are statistically significant. As this is a phase 2 study, no adjustment for multiplicity will be made for having two co-primary hypotheses.

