5.5. Primary Endpoint(s) Analysis

5.5.1. Definition of Endpoint(s)

Time to Clinical Improvement

Time to clinical improvement will be derived as the earliest date of either not requiring oxygen support or hospital discharge, minus the date of randomization. Participants who die or withdraw from the study prior to observing clinical improvement will be censored on day 28. Participants will be censored on day 28, if clinical improvement has not been observed by this time point. If a participant discontinues study drug early, they will still be assessed for this endpoint until one of the above criteria (i.e., clinical improvement, death/withdrawal, day 28 visit without clinical improvement) is met.

Change from baseline to Day 10 or hospital discharge if sooner, in the ratio of hemoglobin oxygen saturation to inspired oxygen fraction (SpO₂/FiO₂)

SpO₂ and FiO₂ will be collected twice daily while a participant is in hospital. The average of the twice daily SpO₂/FiO₂ ratio will be used for all derivations. If only a single ratio is collected, that single ratio for that day will be used. Once discharged, only a single ratio will be used in the derivations. Participants who are discharged prior to day 10, will have their end of treatment assessment, mapped to day 10.

The SpO₂ value will be recorded on the eCRF. To derive the FiO₂ value, oxygen flow rate as collected on the eCRF will be converted to FiO₂ using the following table.

Method	O2 Flow rate (l/min)	Estimated FiO2 (%)
Nasal cannula	1	24
	2	28
	3	32
	4	36
	5	40
	6	44
Nasopharyngeal catheter	4	40
	5	50
	6	60
Face mask (Simple Mask)	5	40
	6-7	50
	7-8	60
Face mask with reservoir (non-rebreather face mask)	<6	Follow nasal cannula
	6	60
	7	70
	8	80
	9	90
	10	95
	>10	100
Venturi Mask	4	28
	6	31
	8	40
	10	50

The change from baseline to Day 10 or hospital discharge if sooner, in the ratio of hemoglobin oxygen saturation to inspired oxygen fraction (SpO₂/FiO₂) will be derived by taking the SpO₂/FiO₂ ratio at the earlier of day 10 or hospital discharge and subtracting the baseline SpO₂/FiO₂ ratio. Missing data will be assumed to be missing at random and this endpoint will be analyzed using likelihood-based methods, therefore missing data will be maintained as missing.

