5.5.2. Main Analytical Approach

Time to Clinical Improvement

Time to clinical improvement will be presented by treatment group, using the Kaplan-Meier estimator. A Cox proportional hazards model with treatment, remdesivir strata (yes/no) and age (years) as covariates will be used to estimate the hazard ratio and compare treatment groups. Additional covariate's (i.e., Country (USA, Brazil), Chloroquine or hydroxychloroquine use (yes vs no), HIV anti-viral drug use (yes vs no), corticosteroid use (yes vs no) and azithromycin use (yes vs no)) may also be included if these are found to influence the treatment effect, based on observing p-value of < 0.05 for the covariate, after adjusting for the others in the model. The

stepwise selection procedure will be used to assess the additional covariates. In addition, the log rank test and stratified log rank test, with remdesivir as the strata, will be provided. The primary analysis will be conducted using the FAS.

Change from baseline to Day 10 or hospital discharge if sooner, in the ratio of hemoglobin oxygen saturation to inspired oxygen fraction (SpO₂/FiO₂)

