5.5.3. Sensitivity Analysis

Time to Clinical Improvement

The following sensitivity analyses will be conducted:

- 1) The primary analysis will be repeated for the PP analysis set.

Change from baseline to Day 10 or hospital discharge if sooner, in the ratio of hemoglobin oxygen saturation to inspired oxygen fraction (SpO₂/FiO₂)

The following sensitivity analyses will be conducted:

- 1) The primary analysis will be repeated for the MITT analysis set.
- 2) The primary analysis will be repeated for the PP analysis set.

Depending on the amount of missing data, additional sensitivity analyses may be needed. If these are needed, they will be documented in the CSR.

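### The SAP's per-protocol set requires at least six doses although dosing stops at discharge, so adherent participants discharged early are excluded because of a primary-endpoint event

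*SAP*

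**What the plan says.** **The two PP definitions differ.** Protocol 9.3 defines the set as "All randomized subjects who receive at least one dose of study drug without any major protocol violations" affecting the primary endpoints. SAP section 4 raises the minimum to participants "who receive at least 6 doses of study drug without any major protocol violations". The SAP version history neither lists nor explains the change. SAP section 1 says the SAP prevails where the two disagree.

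**Dosing ends at discharge.** SAP 1.2 gives "study drug in combination with SOC over 10 days (through Day 10/end of treatment) or until hospital discharge, if sooner", and the protocol's Schedule of Activities adds "Treatment to be administered during hospitalization only". The regimen in protocol 6.1 is "900 mg BID (6 capsules BID) for a total of 1800 mg per day".

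**Discharge is an endpoint event.** SAP 5.5.1 derives time to clinical improvement as the "earliest date of either not requiring oxygen support or hospital discharge, minus the date of randomization".

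**Use of the set.** SAP 5.5.2 states for both primary endpoints: "The primary analysis will be conducted using the FAS". SAP 5.5.3 then lists, for each of them, "The primary analysis will be repeated for the PP analysis set". For time to recovery this is the only sensitivity analysis listed. For SpO₂/FiO₂ it is one of two, the other using the MITT set. No supplementary analyses are planned (SAP 5.5.4).

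**The concern.** A per-protocol set is meant to keep the people who followed the protocol. Someone who takes every dose offered and is discharged before the sixth has done so, yet the SAP's rule leaves that person out. What excludes them is a good outcome that counts as an event in one primary endpoint and fixes the assessment time in the other. No exception is written.

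The SAP expects short stays. It tabulates exposure of 0-3 days as a category (5.8.1), and it maps the end-of-treatment SpO₂/FiO₂ value of early discharges to Day 10 so that they contribute to that endpoint (5.5.1). The PP repeat then drops the earliest of them.

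At stake is how the sensitivity analysis can be read. If the FAS and PP results differ, the reader cannot tell whether adherence and protocol violations explain it or whether early discharges were selected out. If treatment shortens early stays, that selection is also unequal between the arms.

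**Working it through.** **1. When the sixth dose falls.** With twice-daily dosing, doses one to six fall at 0, 0.5, 1, 1.5, 2 and 2.5 days after the first. Six doses therefore take 2.5 days to reach and make up three full days of dosing. Both cut-offs are used below.

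**2. The plan's own figure.** SAP section 3 takes two-sided 5%, 80% power, one third on control and a ratio of 0.5. Events = (1.960 + 0.842)² / [(1/3)(2/3)(ln 0.5)²] = 7.849 / (0.2222 × 0.4805) = 73.5, so 74; 75 events give 80.8% power. This agrees with the stated 75. (It needs θ = log 0.5; the inverse, as printed, gives 17. That is a separate matter.) The documents give no figure for exclusions under the six-dose rule.

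**3. Exclusions at the design assumptions.** Inputs from SAP section 3: placebo median 12-15 days, time halved on active (recovery rate ratio 2), 40 control and 80 active. Assumptions not in the documents: exponential times, and discharge on the day of recovery. Then P(out by day t) = 1 − 0.5^(r·t/median), with r = 1 on placebo and r = 2 on active.

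| Placebo median | t (days) | Placebo | Active | Excluded of 120 |
|---|---|---|---|---|
| 12 | 3 | 15.9% (6.4) | 29.3% (23.4) | 29.8 |
| 15 | 3 | 12.9% (5.2) | 24.2% (19.4) | 24.5 |
| 12 | 2.5 | 13.4% (5.4) | 25.1% (20.1) | 25.4 |
| 15 | 2.5 | 10.9% (4.4) | 20.6% (16.5) | 20.9 |

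With no treatment effect, both arms lose the same share (12.9-15.9% by Day 3). The table counts early recoverers only.

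**4. Calibrated to the planned events.** The medians in step 3 imply 103-109 events by Day 28 (29.0 + 74.0 at a median of 15; 32.1 + 76.9 at 12), well above 75. Solving 40(1 − e^(−28λ)) + 80(1 − e^(−56λ)) = 75 gives λ = 0.0220 per day. By Day 3, placebo is 1 − e^(−3λ) = 6.4% and active is 1 − e^(−6λ) = 12.3%, so 2.6 + 9.9 = about 12 participants (about 10 at 2.5 days). That λ implies a placebo median of ln 2/λ = 31.6 days. The SAP's median and event count therefore do not fit together under exponential times. The SAP does say at least 75, so the two calibrations are best read as a range.

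**5. If discharge lags recovery.** This was simulated with a placebo median of 13.5 days, rate ratio 2, a 3-day cut-off and an assumed exponential lag. A mean lag of 2 days excludes 6.8% of placebo and 13.2% of active (0.068 × 40 + 0.132 × 80 = 13.3 participants). A mean lag of 5 days excludes 3.6% and 6.8% (6.9 participants). The active arm still loses about twice the share.

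**6. Effect on the PP result.** Cox models on simulated data, placebo median 13.5 days. The early effect is an assumption: rate ratio 4 to Day 3, then 1.5.

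| Scenario | Mean lag (days) | Cox rate ratio, FAS → PP | Ratio of medians, FAS → PP | Events per 120, FAS → PP |
|---|---|---|---|---|
| Proportional hazards | 0 | 2.01 → 2.01 | 2.02 → 1.69 | 106 → 79 |
| Proportional hazards | 2 | 1.99 → 1.99 | 1.99 → 1.82 | 106 → 93 |
| Early effect | 0 | 2.04 → 1.52 | 3.47 → 1.39 | 104 → 62 |
| Early effect | 2 | 2.03 → 1.82 | 3.40 → 1.98 | 104 → 82 |

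No figure was derived for SpO₂/FiO₂.

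**The case against.** **The planned estimator may not be biased.** This stands under proportional hazards, where dropping everyone who recovers before a fixed day leaves the Cox ratio unchanged. What remains is the loss of events, the shift in medians, and attenuation if the effect is early.

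**The rule does not simply remove the fastest recoverers.** A reader might infer that it does, but it acts on doses received. Someone who comes off oxygen and stays in hospital on drug has recovered and is kept. Discharge readiness also requires absence of fever and recovery of mobility, dressing and diet (protocol 8.1.5), so discharge may lag. Early deaths, withdrawals and drug stoppers are removed too, and those are often poor outcomes.

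**The better arm does not always lose more.** A larger share is lost only if the arms differ in discharge before the sixth dose. An arm that does better only later loses no larger share for this reason.

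**A minimum exposure is a common PP requirement, and little rests on this set.** Both primary analyses use the FAS, and SAP 5.5.2 adds log-rank and stratified log-rank tests. But six doses serves the exposure aim poorly: it keeps someone who stops drug on Day 4 while still in hospital and drops an adherent early discharge.

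**The document difference is already governed.** Protocol 9.4 lets the SAP modify its plans, and the SAP prevails. That settles which rule applies, not whether the rule is sound.

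**An 80% compliance rule already exists (SAP 5.4, 5.9.7).** It does not lift the six-dose minimum. Its denominator ends at the last dose taken, so an early stopper can score 100%. It also counts whole days: four consecutive doses from Day 1 evening to Day 3 morning score 24 of 36 capsules, or 67%.

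**Conclusion.** The point holds for the PP sensitivity analyses of the two primary endpoints. As written, SAP section 4 excludes adherent participants because of early discharge.

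The size is uncertain. By Day 3 it ranges from about 4% of placebo and 7% of active (assumed 5-day mean lag) to an upper bound of 13-16% and 24-29% (25-30 of 120; about 21-25 at 2.5 days). Calibrated to 75 events it is about 6% and 12%. All of this rests on exponential times and a recovery rate ratio of 2; the lag and the early-effect scenario are also assumptions.

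Two stronger readings are tempting, and the documents do not support them. One is that any PP-FAS difference would be an artefact: PP also drops wrong intervention, non-compliance, prohibited medication and other major violations, so a difference could have several causes. The supportable statement is that it could not be told apart from this selection. The other is that the trial's primary result is affected: it is not, because both primary analyses use the FAS.

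This is a worthwhile, inexpensive correction to a supportive analysis.

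**What to change.** In SAP section 4, replace the six-dose minimum with: received at least 80% of the individual doses due from first dose to the earliest of discharge, death or Day 10, with discharge counted as completing treatment, and no major protocol violation affecting the primary endpoints. Use the same definition in protocol 9.3.

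Count doses due, not whole days, and let doses missed while still in hospital count against the participant. Apply this measure to the non-compliance violation in SAP 5.4 as well; otherwise the formula in 5.9.7 could exclude some of the same early discharges by another route. Report PP exclusions by arm and reason.

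The cost is one definition, its matching text and a small programming change, with no new data to collect. The downside is that PP will include a few participants with short exposure. Restoring the protocol's one-dose rule would also remove the selection but gives up the exposure aim.
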